**Study Protocol**

**University Of Pittsburgh IRB STUDY22020096 Approved 4/5/2022**

At Magee, based on medical records, pregnant and postpartum women meeting the study eligibility criteria will be asked to join the study. Following enrollment, mothers will be randomized to one of two groups: FCU-Heart (intervention) or FCU Alone (usual care comparison). The FCU begins with an assessment of parent-child interaction quality, caregiver psychological resources and support, and child risk/promotive factors. FCU assessments are typically one hour in length; using only 30 minutes to complete the FCU alone ecological assessment provides another 30 minutes for evaluating maternal and infant CVH.

**Intervention:** A Family Check-Up family coach will meet with families for a “check-up” about the child’s development and behavior and how to improve their own well-being to support the child’s development. The Family Check-Up typically takes place over the course of 3-5 sessions, each about an hour long. These meetings take place at home or wherever is most convenient including virtually online.

- First, a trained Family Check-Up family coach will conduct an “Initial Interview.” The second step is completing questionnaires about the child and family relationships and social support. An important part of this second step is the family interaction tasks, where mother and child will take part in activities like playing together with toys and puzzles. The Family Check-Up family coach will then highlight parenting strengths during the third meeting, called the Feedback Session.
- Assessments also include measurement of your blood pressure, body mass index, diet quality, exercise, smoking. During the Feedback Session, the Family Check-Up family coach will meet with you for a conversation about strengths and challenges for your child and family as a whole. You’ll be invited to set goals for you and your child to support and maintain strengths, and to address any areas of concern.
- After the Feedback Session families have the option to continue meeting with your family coach to support the child’s development and improve parental well-being.

Participants randomly selected to participate in the Family Check-Up Heart program will also receive information about healthy eating and weight loss, stress management, and smoking and to monitor weight and blood pressure. ENRICH foundational modules will be incorporated as appropriate.

**Maternal CVH:** BP and BMI will be assessed using validated Bluetooth devices and following standardized research protocols. Diet quality will be assessed using the Rapid

Eating Assessment for Participants (REAP-S). Physical activity in mothers will be assessed using (1) the Pregnancy physical activity questionnaire (PPAQ), which measures active and sedentary behavior and (2) bluetooth data from Fitbit devices using standardized research protocols. Smoking will be assessed via questionnaire. These measures allow feedback by the family coaches.

The blood pressure and weight data measured by the iHealth devices is transmitted via Bluetooth to the participant's personal device and loaded into the installed iHealth app. From there, the iHealth app securely transmits the BP data to the participant's iHealth cloud account. Our team will make API requests to download the data from the iHealth cloud to a secure UPMC server and upload it to a REDCap database. The same process will be used to collect Fitbit activity data from the Fitbit app and cloud account. Data transfer over the internet using either the iHealth Cloud API, the Fitbit API, or the REDCap API is secure and encrypted (using the HTTPS protocol). The iHealth and Fitbit cloud data access are authorized at the time of recruitment and are valid for one year. The participant is also able to revoke the access anytime in her iHealth cloud account or the Fitbit cloud account.

Outcomes CVH assessments at 6 months will be conducted remotely when possible for the FCU Alone control group. Control group participants will be sent a body weight scale and BP cuff when they are due for their 6 month measurements. After they receive them, staff will facilitate the measurements virtually and let them keep the devices. We will do in person assessments only as needed, and will provide the scales and BP cuffs to keep at study conclusion.

All participants will be given a handout from NHLBI (uploaded in local supporting documents section) at the study conclusion after they complete the 6-month outcomes assessment. They will also be provided with the American Heart Association's web page that addresses understanding blood pressure readings. If the outcome readings are elevated or high, they will also be advised to consult with their doctor.

Child CVH will be assessed with BP and BMI. BP will be measured following a standardized research protocol using a pediatric-sized cuff.

Implementation measures. We will assess the implementation of the FCU-Heart by collecting data on key implementation measures based on modified FRAME-IT model for early intervention (includes feasibility, reach,

acceptability, maintenance, equity, implementation, and tailorability). At the completion of the FCU and FCU-Heart interventions (6 months), participants will complete a brief acceptability and satisfaction survey, including the Working Alliance Inventory. We will conduct qualitative interviews with FCU-Heart family coaches to assess their perspectives on feasibility, appropriateness of the intervention, and barriers/facilitators of implementation. Program enrollment and completion of sessions will be used to assess feasibility and family engagement. The digital literacy scale will also be administered at 6 months to test whether this construct has an impact on overall engagement in intervention or on engaging in remote/virtual intervention sessions vs in person.

All participants in both groups will receive referral for additional services based on needs identified during the FCU (e.g., developmental services/ Early Intervention, parent/child mental health). In addition, we will communicate findings from assessments performed as part of the FCU and facilitate communication with pediatric providers and/or referrals following the Pitt pediatric teams' routine practice. Participants in the control group who are identified as having elevated blood pressure will be given a handout from NHLBI (uploaded in local supporting documents section) and will be advised to consult with their doctor.

Protected health information (PHI) will be collected for the proposed research project. Participants will be asked to provide access to their electronic medical records (EMRs) and their child's electronic medical record (EMR) during the informed consent process. Upon enrollment in the study, all participants will be assigned a unique study identifier; this study ID is used in place of identifying PHI on all study documents with the exception of the informed consent form.

After a participant gives birth, the study team will mail a greeting card congratulating them on the birth of their baby.

In the event that a participant loses their pregnancy or their infant, the study team will send a greeting card expressing sympathy and offering referrals to grief support, if desired. The participant will be withdrawn from the study.

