**Expanding the Family Check-Up in Early Childhood to Promote Cardiovascular Health
of Mothers and Young Children (NCT05473767)**

Data Analysis Plan

University Of Pittsburgh IRB STUDY22020096 Approved 4/5/2022

As it is a pilot study, the focus will be on the estimation of the difference in mean levels of blood pressure and weight between women in FCU-Heart and FCU alone. Let δ be the intervention effect, representing the difference in mean BP and weight at 6 months between the two intervention arms. The mean difference δ will be estimated first by separately estimating the group means using observed sample means, and then taking a difference of the observed sample means. We will use two-sample t-distribution to construct a 95% confidence interval of the estimated δ to quantify the uncertainty in the estimation. The analysis will be repeated for each race stratum. With 100 participants in FCU-Heart and 50 in the standard FCU group, we will be able to estimate δ with a margin of error of 13.7% with 95% confidence, assuming a standard deviation of 40% in both populations. The sample sizes are sufficient to detect an effect size of 0.5 with 82% power at 5% level of significance. An effect size of 0.5 is consistent with intervention effects from the first early childhood FCU RCT on both parenting ($d=.48$) and child problem behavior ($d=.64$) 1-2 years post-intervention. Based on attaining 90% retention for the 6-month follow-up of the TPS-FCU study and our CVH intervention, we expect that our retention will also be ~90%. All the analyses will follow intention-to-treat principle (analyzed as randomized).

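### The only time point given for the digital literacy scale is 6 months, after engagement has accrued, so the stated impact of literacy on engagement cannot be told from the reverse

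*Protocol*

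**What the plan says.** The Protocol's paragraph on implementation measures gives the timing and purpose of the scale: "The digital literacy scale will also be administered at 6 months to test whether this construct has an impact on overall engagement in intervention". The sentence goes on to name a second target, remote or virtual sessions versus in-person ones.

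Three other statements fix the time order:

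- The acceptability survey is placed by the words "At the completion of the FCU and FCU-Heart interventions (6 months", so 6 months is the end of both programmes.
- Engagement is defined in the same paragraph: "Program enrollment and completion of sessions will be used to assess feasibility and family engagement".
- The Intervention section describes what accrues before then: "The Family Check-Up typically takes place over the course of 3-5 sessions", and on location, "These meetings take place at home or wherever is most convenient including virtually online".

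The SAP does not mention digital literacy. Its stated purpose is different: "As it is a pilot study, the focus will be on the estimation of the difference in mean levels of blood pressure and weight".

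**The concern.** Claiming that literacy has an impact on engagement requires, at the least, that literacy be measured before engagement happens. Here the score is taken once, when the sessions are over. Neither document gives an earlier administration or a reason to treat the score as stable over the period.

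The Protocol itself supplies routes for the reverse path. Women may attend online, which is practice with digital tools. The Maternal CVH section describes blood pressure, weight and activity data passing through iHealth and Fitbit apps, with cloud access authorized at recruitment. It also says that controls are sent a scale and cuff only when their 6-month measurements are due, so digital exposure may differ by arm.

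A second, smaller matter is that women without a 6-month assessment have no score. They may be among the less engaged, although the documents do not say so.

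At stake is a pilot finding about whether low digital literacy is a barrier to engagement or to virtual delivery. A positive result could be read as a barrier to target when it is partly a product of taking part.

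**Working it through.** The documents give no figure for this analysis, so there is none to reproduce. The check has two parts: time order, and an illustration of what a reverse effect would do.

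**Time order.** Outcome (sessions completed, session mode): accrues from the start of the programme to 6 months. Predictor (literacy score): 6 months. The predictor does not precede the outcome for either target.

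**Inputs.** The SAP gives the arm sizes, "With 100 participants in FCU-Heart and 50 in the standard FCU group", and expected retention of about 90%. Women with a 6-month score: 0.90 × 150 = 135, of whom 0.90 × 100 = 90 are in FCU-Heart. Women without one: 150 − 135 = 15. The reverse effect *b* is assumed; the documents give no value.

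**Model.** Let L0 be literacy at enrolment and E engagement, independent of each other, each with SD 1. Literacy therefore has no true effect on engagement. The 6-month score is L6 = L0 + bE, which gives

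r = corr(L6, E) = b / √(1 + b²).

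If literacy instead drives engagement and is stable (E = bL0 + noise with SD 1, L6 = L0), the correlation is the same b / √(1 + b²). One score at the end cannot separate the two cases.

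**Chance of a significant correlation** (two-sided 5%, Fisher z): m = atanh(r) × √(n − 3), and P = Φ(m − 1.96) + Φ(−m − 1.96). With n = 135, √132 = 11.489.

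| b | r | m | P |
|---|---|---|---|
| 0.05 | 0.050 | 0.574 | 0.089 |
| 0.1 | 0.100 | 1.147 | 0.209 |
| 0.2 | 0.196 | 2.283 | 0.627 |
| 0.3 | 0.287 | 3.397 | 0.925 |

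With b = 0 the rate is 0.05. Simulation (40,000 trials per setting) agrees: 0.090, 0.209, 0.628, 0.926.

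**Sensitivity to the assumptions** (simulated, n = 135, b = 0.05 / 0.1 / 0.2 / 0.3):

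- E taken as 3, 4 or 5 sessions with equal probability: 9%, 21%, 63%, 93%.
- Reverse effect in FCU-Heart only (90 of 135), arms pooled: 7%, 12%, 33%, 62%.
- Reverse effect only in women attending virtually, unrelated to session count, with an assumed virtual share of 50%: 6%, 9%, 21%, 40%. With a 30% share: 5%, 7%, 11%, 18%.
- Session mode as the outcome, standardized to SD 1: 9%, 21%, 63%, 93%.

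**Limit of an enrolment score.** With no effect in either direction, a trait correlated *a* with both literacy and engagement gives r = a². With n = 150, √147 = 12.124:

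- a = 0.3: r = 0.09, m = 1.094, P = 0.194.
- a = 0.5: r = 0.25, m = 3.097, P = 0.872.

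An earlier score therefore fixes the order in time and leaves confounding in place.

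**The case against.** The strongest reply is about size and weight.

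**An enrolment score may exist.** Its absence is inferred from silence, and the Protocol has no schedule of assessments. That stands as a caution. Even so, 6 months is the only time point given, and if there is an earlier score the sponsor need only say so.

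**Sessions do not teach digital skills.** The content described is interview, questionnaires, play tasks, feedback and goal-setting, so an in-person session has no documented route to a higher score. App use would matter only so far as it tracks sessions completed or arm. This stands for session count, where the lower virtual-only rates are arguably the more realistic ones. It is weak for session mode, where attending online is itself the exposure.

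**The repair gains little, because confounding remains.** It is true that neither timing supports a claim of impact. But an enrolment score does remove one of the competing explanations and covers the roughly 15 women who would otherwise have no score.

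**No document specifies a significance test for literacy.** Correct. The rates show how readily a misleading association could arise; they are not the error rate of a planned test. The 3-to-5-session check also leaves out women who never start or who leave early.

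**Conclusion.** The concern holds. As written, the plan scores the stated predictor after its outcome, and the result cannot support a statement that literacy has an impact on engagement or on session mode. This conclusion rests on the timing alone.

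The size is uncertain. At b = 0.05 the problem is close to negligible in every scenario. At b = 0.2 the chance of a misleading association in session count ranges from about 11% (reverse effect confined to a 30% virtual share) to 63% (all women). All these rates depend on assumed values of b and, where used, of the virtual share.

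This is an improvement to consider in an ancillary aim. The blood pressure and weight estimates, session counts, acceptability survey and coach interviews are not affected.

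**What to change.** Give the scale at enrolment in both arms, before randomization and the Initial Interview; the Protocol already places enrolment first ("Following enrollment, mothers will be randomized to one of two groups"). Use that score as the predictor of sessions completed and, among women who attended at least one session, of session mode. Analyse by arm or adjust for arm. Report an estimate with a confidence interval, described as an association open to confounding.

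For women already enrolled, or if the scale cannot be moved, reword the aim as an association among women assessed at 6 months, reported by arm, with no inference of direction.

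The first option costs a small amendment and one more questionnaire at enrolment. The scale is not named and its length is not given, so the burden is unknown, and completing it before randomization adds a step the Protocol does not now describe. The second option costs a change of wording.

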**Expanding the Family Check-Up in Early Childhood to Promote Cardiovascular Health
of Mothers and Young Children (NCT05473767)**

Data Analysis Plan

University Of Pittsburgh IRB STUDY22020096 Approved 4/5/2022

As it is a pilot study, the focus will be on the estimation of the difference in mean levels of blood pressure and weight between women in FCU-Heart and FCU alone. Let δ be the intervention effect, representing the difference in mean BP and weight at 6 months between the two intervention arms. The mean difference δ will be estimated first by separately estimating the group means using observed sample means, and then taking a difference of the observed sample means. We will use two-sample t-distribution to construct a 95% confidence interval of the estimated δ to quantify the uncertainty in the estimation. The analysis will be repeated for each race stratum. With 100 participants in FCU-Heart and 50 in the standard FCU group, we will be able to estimate δ with a margin of error of 13.7% with 95% confidence, assuming a standard deviation of 40% in both populations. The sample sizes are sufficient to detect an effect size of 0.5 with 82% power at 5% level of significance. An effect size of 0.5 is consistent with intervention effects from the first early childhood FCU RCT on both parenting ($d=.48$) and child problem behavior ($d=.64$) 1-2 years post-intervention. Based on attaining 90% retention for the 6-month follow-up of the TPS-FCU study and our CVH intervention, we expect that our retention will also be ~90%. All the analyses will follow intention-to-treat principle (analyzed as randomized).

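### The SAP compares raw 6-month means across women enrolled pregnant and postpartum, with no time origin and no adjustment for time from delivery

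*SAP*

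**What the plan says.** **Who enters.** The opening section of the Protocol says that "pregnant and postpartum women meeting the study eligibility criteria will be asked to join the study", and then "Following enrollment, mothers will be randomized to one of two groups". The end of the Protocol confirms that some women are still pregnant at entry: "After a participant gives birth, the study team will mail a greeting card congratulating them on the birth of their baby". It also provides for pregnancy loss on study: "In the event that a participant loses their pregnancy or their infant, the study team will send a greeting card". The supplied text gives no gestational or postpartum window and no expected shares.

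**When the outcome is taken.** The time point is named three times, each time without an origin:
- SAP, Data Analysis Plan: δ is described as "representing the difference in mean BP and weight at 6 months between the two intervention arms".
- Protocol, Maternal CVH: "Outcomes CVH assessments at 6 months will be conducted remotely when possible for the FCU Alone control group".
- Protocol, Implementation measures: "At the completion of the FCU and FCU-Heart interventions (6 months". This ties 6 months to the end of the intervention, but the start is not dated either.

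**How δ is estimated.** The SAP subtracts one observed sample mean from the other and puts a two-sample t interval around the result. The only further analysis repeats this within race strata. Neither document mentions a covariate, a stratum, a subgroup or a visit window for pregnancy status or time from delivery.

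**The concern.** Body weight changes substantially through pregnancy and after delivery, and BP may change too. In this cohort, a woman's place on that course at the outcome visit depends on when she enrolled and on which clock is used. The SAP averages all these values as one quantity.

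Two things are at stake. First, a reader cannot tell whether δ for weight describes early postpartum weight, later retained weight or partly weight in pregnancy. A follow-on trial could not safely reuse its mean or SD. Second, time from delivery at enrolment is likely to be strongly prognostic and is known before randomisation, yet the unadjusted estimator leaves its contribution in the error term. The SAP makes estimation of δ the focus of this pilot, so both interpretability and precision matter.

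**Working it through.** **1. The plan's own figures.** Inputs from the SAP: 100 and 50 women, SD 40%, effect size 0.5, 5% level (taken as two-sided).
- Margin of error: t(0.975, 148 df) × 40 × √(1/100 + 1/50) = 1.976 × 6.928 = 13.69%. The stated 13.7% reproduces.
- Power: Φ(0.5/√(1/100 + 1/50) − 1.96) = Φ(0.927) = 82.3%; the noncentral t gives 81.8%. The stated 82% reproduces.

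Neither figure depends on pregnancy status, so they do not settle this point.

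**2. What each clock implies.** Take 6 months as 26 weeks and delivery at 40 weeks (assumptions).

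| Gestation at enrolment | 26 weeks after enrolment |
|---|---|
| 12 weeks | 38 weeks' gestation |
| 14 weeks | 40 weeks, the turning point |
| 20 weeks | 6 weeks postpartum |
| 28 weeks | 14 weeks postpartum |
| 36 weeks | 22 weeks postpartum |
| Enrolled postpartum | more than 26 weeks postpartum |

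- *Clock from enrolment:* values in pregnancy arise only with entry before about 14 weeks (14 + 26 = 40). Even without such entries, times since delivery can differ by months.
- *Clock from delivery:* all values are postpartum, but time since randomisation varies instead. A woman enrolled at 14 weeks would be measured 26 + 26 = 52 weeks after enrolment. One enrolled postpartum would have less than 6 months of follow-up.
- *Clock from the first FCU assessment:* the Protocol says "The FCU begins with an assessment of parent-child interaction quality", which suggests a start after birth and so no value from the index pregnancy. Time since delivery would still vary with the child's age at that first session.

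The clock determines what is mixed. On each reading, either time since delivery or time since randomisation can vary with when the woman enrolled.

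**3. Effect on the interval for weight.** Assumed, not in the documents: a share p of 30% to 50% in a different state, a gap g of 5 to 10 kg, and a total weight SD of 15 to 25 kg. With the SAP's 90% retention, 90 and 45 women remain.
- Unadjusted half-width: 1.978 × SD × √(1/90 + 1/45) = 5.4 kg (SD 15) to 9.0 kg (SD 25).
- Mixture variance p(1 − p)g²: 0.3 × 0.7 × 25 = 5.25 kg², up to 0.5 × 0.5 × 100 = 25 kg².
- Width ratio if all of it is removed: √(1 − mixture variance/SD²).

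| Mixture variance | SD 15 | SD 25 |
|---|---|---|
| 5.25 kg² | 0.988 (1.2% narrower) | 0.996 (0.4% narrower) |
| 25 kg² | 0.943 (5.7% narrower) | 0.980 (2.0% narrower) |

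This counts only the difference between two states. It assumes the model removes all of that difference, and it ignores spread in timing within each state.

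**4. The same in power terms.** Hold the effect at 0.5 within-state SDs with 100 and 50 women (normal approximation). The pooled SD grows by √(1 + p(1 − p)g²), with g now in within-state SDs. The assumptions in step 3 give g from 5/√(625 − 5.25) = 0.20 to 10/√(225 − 25) = 0.71. Power is then 82.0% (p = 0.3, g = 0.20) to 77.7% (p = 0.5, g = 0.71), against 82.3%. A full 1-SD gap, outside that range, gives 79.0% to 73.3% for p from 0.10 to 0.50.

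**5. Chance imbalance.** The 95% range of the shift in δ is ±1.96 × g × √[p(1 − p)(1/90 + 1/45)], with g in kg. It is ±0.82 kg for p = 0.3 and 5 kg, and ±1.79 kg for p = 0.5 and 10 kg.

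**The case against.** The strongest reply is that the documents do not show a single pregnancy weight entering δ. That needs both an enrolment clock and entry before about 14 weeks, and neither is documented. The full eligibility criteria are not in the supplied text and may set a window. The parent-child content at the start of the FCU, with 6 months equated to the end of the intervention, points if anything to a clock starting after birth. All of this stands. A reader might infer that δ does mix gestational and postpartum weights, but the documents support only that it may.

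A reader might also infer bias. There is none in expectation: the arms are randomised and compared at the same nominal time. Nor is the ±0.82 to ±1.79 kg imbalance an extra error on top of the reported interval, because the planned t interval already includes it. The larger figures also rest on a pregnant-versus-postpartum gap for 30% to 50% of women. The documents support no such share, and gaps between different postpartum times could be smaller. No figure is available for BP.

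The reply does not remove the core of the point. Entry is mixed, the time origin is unstated, and the estimator ignores a prognostic variable known before randomisation. Defining the origin alone would make the timing explicit, but the related variance would remain in the interval.

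**Conclusion.** The point holds as one of interpretability and precision. As written, δ may combine different times since delivery, and possibly some values in pregnancy, depending on a clock and an entry window that the supplied text does not give. It is not a finding of bias, and it does not establish that pregnancy values are present.

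Under the assumed shares, gap and SD, the interval for weight would narrow by about 0.4% to 6%, which is modest. The gain may be larger if baseline weight is also in the model, because the remaining error is then smaller and baseline weight itself carries pregnancy weight. That gain cannot be sized from the documents. The change is worth making because it costs almost nothing and gives δ for weight a clearer meaning.

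**What to change.** - **Estimator.** For both weight and BP, estimate δ from a linear model with arm, enrolment status (pregnant or postpartum) and weeks before or after (expected) delivery at enrolment. Report the 95% interval from that model. For women enrolled pregnant, use the delivery date expected at enrolment, so that every covariate is fixed before randomisation and the analysis stays as randomised.
- **Secondary, descriptive.** Report δ for weight separately by enrolment status, noting that these intervals will be wider with about 45 retained controls in all.
- **Time origin.** State one origin for the 6 months and use it in the SAP and in the Maternal CVH and Implementation measures paragraphs of the Protocol. The choice is the sponsor's.
- **What to avoid.** Do not exclude women, or split the analysis, by whether they are pregnant at the outcome visit. That status is determined after randomisation and would cut across the SAP's intention-to-treat commitment.

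The cost is a few sentences in the SAP, matching wording in the Protocol, and two baseline variables. The Protocol already recruits from medical records and asks for record access at consent, so these should need no new data collection.

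### The SAP analyses 6-month weight without using height and leaves unanalysed the BMI that the protocol names; adjusting for height and reporting BMI is a cheap, modest gain in precision

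*SAP*

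**What the plan says.** **Protocol.** Under Maternal CVH: "BP and BMI will be assessed using validated Bluetooth devices and following standardized research protocols". The second bullet under Intervention also lists BMI: "Assessments also include measurement of your blood pressure, body mass index, diet quality, exercise, smoking". When the Maternal CVH section turns to data capture, it speaks of weight: "The blood pressure and weight data measured by the iHealth devices is transmitted via Bluetooth". For the 6-month outcome assessment in the FCU Alone arm: "Control group participants will be sent a body weight scale and BP cuff when they are due for their 6 month measurements". No height measurement is described, and no maternal measure is labelled primary.

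**SAP, Data Analysis Plan.** δ is defined as "representing the difference in mean BP and weight at 6 months between the two intervention arms". It is obtained by estimating each arm's mean and "then taking a difference of the observed sample means". For the interval: "We will use two-sample t-distribution to construct a 95% confidence interval of the estimated δ". The sample size statement begins "With 100 participants in FCU-Heart and 50 in the standard FCU group". It gives a 13.7% margin of error for an SD of 40%, 82% power for an effect size of 0.5 at the 5% level, and expected retention of about 90%. BMI, height and covariates are not mentioned.

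**The concern.** The two documents name different body-size measures. The choice matters more here than in many trials because δ compares different women at one time point. In an analysis of within-woman change, weight and BMI would carry nearly the same information, since adult height is fixed. In a comparison of raw 6-month means, taller women weigh more whatever programme they receive, and that variation sits in full in the SD used for the interval.

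Two things are at stake. The measure that the protocol names gets no analysis. And in a pilot whose stated aim is estimation, the interval for weight is wider than it need be, although height, which any BMI requires, could remove part of the noise.

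**Working it through.** **1. The SAP's own figures** (100 and 50 women; two-sided 5% assumed, as sidedness is not stated).
- √(1/100 + 1/50) = 0.1732. Margin = t(0.975, 148 df) × 40 × 0.1732 = 1.976 × 6.928 = 13.69, against 13.7 stated.
- Noncentrality for d = 0.5 is 0.5/0.1732 = 2.887. Noncentral-t power is 81.8% (82.3% by the normal approximation), against 82% stated.
- At 90% retention (90 and 45): √(1/90 + 1/45) = 0.1826, and power is 77.6%.

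Both stated figures hold. They are on a percentage or standardised scale and are not tied to weight or to BMI.

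**2. How much of the weight variance is height.** Assumptions, none of them in the documents: mean height 163 cm, SD 6 to 7 cm; BMI mean/SD from 28/5 to 32/8; BMI independent of height; height recorded without error. With weight = BMI × height², to leading order:
- CV²(weight) = (1 + CV²(BMI)) × (1 + 4CV²(height)) − 1
- r² between weight and height ≈ 4CV²(height) / CV²(weight)
- adjusting for height multiplies the standard error of δ by √(1 − r²)

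| Height SD; BMI mean/SD | 4CV²(height) | CV²(weight) | r | √(1 − r²) |
|---|---|---|---|---|
| 6 cm; 28/5 | 0.0054 | 0.0375 | 0.38 | 0.925 |
| 7 cm; 28/5 | 0.0074 | 0.0395 | 0.43 | 0.902 |
| 6 cm; 32/8 | 0.0054 | 0.0683 | 0.28 | 0.960 |

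Height therefore accounts for about 8 to 19% of the variance of weight, and adjustment lowers the standard error by about 4 to 10%.

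**3. In kilograms at 90:45.**
- 28/5 with height SD 6 cm: mean weight is about 74.5 kg and SD = √0.0375 × 74.5 ≈ 14.4 kg. The standard error is 14.4 × 0.1826 ≈ 2.63 kg unadjusted and 2.63 × 0.925 = 2.43 kg adjusted.
- 32/8 with height SD 6 cm: mean about 85.1 kg, SD ≈ 22.2 kg. The standard error is about 4.06 kg unadjusted and 3.89 kg adjusted.
- With t ≈ 1.98, the 95% half-width goes from about 5.2 to 4.8 kg in the first case and from about 8.0 to 7.7 kg in the second.

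**4. Chance height imbalance at 90:45.** The standard error of the height difference between arms is 6 × 0.1826 = 1.10 cm to 7 × 0.1826 = 1.28 cm. At 0.91 to 1.04 kg per cm (simulated slope), one standard error of imbalance moves δ for weight by about 1.0 to 1.3 kg. The full standard error is about 2.6 to 4.1 kg and already includes this.

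**5. Power, if d = 0.5 is the effect on raw weight.** The effective d becomes 0.5/0.960 = 0.52 to 0.5/0.902 = 0.55.
- 100:50: from 81.8% to about 85-89%.
- 90:45: from 77.6% to about 81-85%.
- If the weight-height correlation is only 0.2: 83.3% and 79.2%.

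**6. BMI in place of weight.** With wider assumptions (CV of BMI 20 to 30%, CV of height 3 to 5%), the relative standard error is 2 to 11% lower on BMI than on weight, a gain of similar size.

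**The case against.** **The SAP's choice of weight has support in the protocol.** The devices capture weight, the 6-month kit for FCU Alone is a scale and a cuff, and FCU-Heart includes weight-loss content. A reader might infer that the protocol defines BMI as the outcome and that the SAP analyses the wrong variable. The documents do not support that: BMI is listed among the things assessed, and the same section says that these measures serve coach feedback. This part of the objection stands, so weight should stay in the SAP.

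**Height is noise, not bias.** A reader might also infer that a height difference between arms would be mistaken for a programme effect. Randomisation balances height in expectation, and chance imbalance is part of the weight SD and so of the t interval. This stands too.

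**The gain is small and rests on assumptions.** The documents give no SD for weight, BMI or height, and the SAP justifies 0.5 from parenting and child-behaviour effects, not from weight. If 0.5 is the effect on BMI or on height-adjusted weight, power there is the same 82%. Error in recorded height would shrink the gain. All of this is fair and limits the weight of the point.

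**Adjusting for entry weight could gain more.** The standard error would be multiplied by √(1 − ρ²): 0.71 at ρ = 0.7 and 0.44 at ρ = 0.9 (ρ assumed). But the documents do not clearly establish a comparable entry weight. Controls are sent scales only when the 6-month reading is due, and women enter either pregnant or postpartum. Height does not depend on the timing of entry or on the programme. The two adjustments can be combined, and entry weight alone would still leave BMI unanalysed.

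**Conclusion.** The point holds as a cheap improvement and not as an error. The protocol names BMI as the maternal body-size measure. The SAP analyses only raw 6-month weight, unadjusted, with no BMI analysis and no use of height. The SAP's estimator is unbiased and its stated power and margin are correct.

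The cost of leaving it is a standard error for weight about 4 to 10% larger than necessary, under the assumed height and BMI distributions with height recorded without error. The power gain of roughly 3 to 8 percentage points needs the further assumption that d = 0.5 applies to raw weight. The cross-document gap, BMI named but not analysed and no stated source for height, needs none of these assumptions.

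**What to change.** In the SAP's Data Analysis Plan:
- Keep 6-month weight. Estimate its δ and 95% CI from a linear model with arm and height, and use the same model in the race-stratum analyses.
- Report the 6-month BMI difference between arms, with its 95% CI, beside the weight result.
- State that BMI uses 6-month weight and one height per woman, taken from the same source in both arms: the entry assessment, or the medical record that participants are asked at consent to open to the study.
- State how a missing height will be handled.

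The cost is a few lines of SAP text and one extra variable per woman, which the protocol's BMI already requires; no extra visit is needed. The downside is small: some women may have no recorded height, or one recorded with error, and this reduces the gain.
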